- 3) To assess the effect of treprostinil inhalation on oxygenation in patients with acute hypoxic respiratory failure with, or at risk for, development of ARDS
- 4) To assess the effect of treprostinil inhalation on various biomarkers thought to be related to the pathogenesis and/or clinical course of ARDS.

We propose a proof of concept, double blinded, placebo controlled study of inhaled treprostinil for patients with "at-risk" or early ARDS. Early, or pre-ARDS will be defined as acute hypoxemia and unilateral pulmonary infiltrates in patients presenting with conditions that are conducive to ARDS (e.g. pneumonia, sepsis, aspiration, trauma) but do not yet meet criteria for ARDS: require mechanical ventilation, bilateral infiltrates on CXR, and PaO_2/FiO_2 ratio < 300. The primary outcome will be PaO_2/FiO_2 ratio. We will also measure other physiologic and clinical outcomes and levels of inflammatory and pro-fibrotic biomarkers. This exploratory initial study will enroll 30 patients to assess feasibility and safety in this population.

Hypothesis:

- 1. Treprostinil inhalation is safe at planned dose titration in patients with acute hypoxemic respiratory failure
- 2. Treprostinil will improve oxygenation and other secondary outcomes related to mechanical ventilation initiation and duration, as well as exhibit effects on ARDS-related pro-inflammatory and pro-fibrotic biomarkers.

Study Design:

- 1) Single Center, proof of concept, 2:1 active drug to placebo controlled, double-blinded
- 2) Target of 30 patients enrolled
- 3) Patients will be randomized to receive either treprostinil or saline inhalation placebo
- 4) Patients will be followed to hospital discharge or day 28, whichever comes first. Those discharged prior to day 28 will be assumed free of mechanical ventilation and alive unless readmitted in that period. This will be confirmed by phone.

Sample Size/Interim Monitoring:

1) This is primarily a feasibility, safety and proof of concept trial.

Version: 02-09-2018

- 2) The primary endpoint is Change in PaO₂/FiO₂ ratio from Study Day 0 to 2, 7
- 3) Trial progress will be monitored by an independent Data and Safety Monitoring Board to determine if the study should stop for safety reasons. The first interim review will occur6 months following enrollment of the first patient or after the first 15 patients (which-ever occurs first) have been enrolled.

Inclusion Criteria:

- 1) Adults age 18-80 years.

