Cough or pharyngitis may occur with the administration of inhaled treprostinil. It is usually mild. The investigator may choose to utilize conservative measures such as topical throat lozenges/spray or non-narcotic based antitussive medications to improve compliance with drug administration.

All enrolled patients will receive standard medical care for their acute presenting illness regardless of randomization group, including but not limited to: antibiotics, IV fluids, supplemental oxygen, and any other needed diagnostic testing or imaging.

*Premature Withdrawal from Treatment:

The following adverse effects should prompt cessation of study drug:

- 1. A drop in oxygen saturation by >/= 10 percentage points, to an absolute value of < 90%, within 15 minutes of drug administration, regardless of apparent relationship to coughing.
- 2. Severe, intractable cough resulting in worsening hypoxemia and prolonged increase in O₂ requirement (Defined as an increase of more than 2LPM O₂ that closely correlates temporarily with the cough.)
- 3. Systemic hypotension requiring increase in vasopressor dose or initiation of vasopressors due solely to the administration of study drug (i.e. not due to underlying illness such as septic shock, as determined per the discretion of the investigator) despite titrating down to previously tolerated level.
- 4. Intubation and mechanical ventilator support
- 5. Need for Bi-level Positive Airway Pressure (BiPAP) or Continuous Positive Airway Pressure (CPAP) via face mask for worsening hypoxemia.

These patients will be followed out to study completion as defined by death, 28 days from randomization, or hospital discharge whichever comes first. Discharged subjects will receive a 28 day post randomization phone assessment of disease outcomes and adverse events.

Completion of Study Drug Administration:

Patients will be considered to have completed the study drug administration portion of the study and the study drug will be stopped when one of the following conditions is met, whichever comes first:

- 1. Up to 12 days after randomization (maximum treatment period)
- 2. Discharge from study hospital. Subjects will receive a 28 day post randomization phone assessment of disease outcomes and adverse events.

3. Death

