The present research will involve subjects who might be vulnerable to coercion or undue influence. As required in 45 CFR 46.111(b), we recommend that additional safeguards be included to protect the rights and welfare of these subjects. Such safeguards might include, but are not limited to: a) assessment of the potential subject's capacity to provide informed consent, b) requirement for subject's assent, c) the availability of the LAR to monitor the subject's subsequent participation and withdrawal from the study, and d) augmented consent processes. The specific nature of the additional safeguards will be left to the discretion of the IRB.

Confidentiality

Federal regulations at 45 CFR 46.111 (a) (7) requires that when appropriate, there are adequate provisions to protect the privacy of subjects and to maintain the confidentiality of data. To

maintain confidentiality, all laboratory specimens, evaluation forms, and reports will be identified only by a coded number. The coded number will be generated at random by a computer, and only the study investigators will have access to the codes. All records will be kept in a locked, password protected computer. All computer entry and networking programs will be done with coded numbers only. All paper case report forms will be maintained in a locked cabinet inside a locked office. Clinical information will not be released without the written permission of the patient, except as necessary for monitoring by the DSMB.

Adverse Event Reporting

Investigators will determine daily if any clinical adverse experiences occur during the period from enrollment through study day 28 or hospital discharge, whichever occurs first. The investigator will evaluate any changes in laboratory values and physical signs and will determine if the change is clinically important and different from what is expected in the course of treatment of patients with ARDS/ALI. If clinically important and unexpected adverse experiences occur, they will be recorded on the adverse event case report form.

For this trial, a reportable adverse event is defined as:

- 1. Any clinically important untoward medical occurrence in a patient receiving study drug or undergoing study procedures which is different from what is expected in the clinical course of a patient with ARDS/ALI, or,

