SBP / MAP (if arterial line is in place otherwise cuff)	Х	х	х	х	х	х	х	х						
Adverse Events Review	х	х	х	х	х	х	х	х	х	х	х	х		
Hospital Mortality														х
Phone Assessment of Disease Outcomes and Adverse Events														х
Day 28 Mortality														Х

Version: 02-09-2018

Appendix 3

Oxygen Titration Protocol

The goal of the Oxygen Titration Protocol is to maintain a resting oxygen saturation of 90-94%. Brief increases in the research subject's O₂ liter flow for ambulation and exertion can be allowed. However, before each study drug administration, the respiratory therapist should make sure that the research subject is on the lowest amount of oxygenation required to achieve an oxygen saturation of 90-94% before recording their baseline O₂ requirement. Reassessment of oxygen saturation before and after each level should occur. Research subjects will start with a conventional humidified nasal cannula. If oxygen titration is needed, we will titrate from their current nasal cannula flow rate in the following stepwise fashion: 4LPM / 5LPM /6LPM. If there is a need for oxygen titration above 6 LPM, we will utilize a High Flow Nasal Cannula with the flow rate of 20 to 50 LPM. We will titrate the High Flow Nasal Cannula FiO2 in the following stepwise fashion: 50%, 60%, 70%, 80%, 90%, and 100%. The required liter flow will be titrated per patient need/demand. If a patient requires more than 50LPM via HFNC, they will have met our classification of *requiring positive pressure threshold*. If clinically indicated, clinicians that are managing the care of these research subjects can initiate non-invasive ventilation or proceed to intubate prior to a patient reaching 100% O₂ or 50LPM flow rate, per our stepwise fashion.

FiO₂ Conversion Table

FIU ₂ Con	version rable
Conventional Humidified Nasal Cannula Flow Rate	FiO ₂
1 LPM	24%
2 LPM	28%
3 LPM	32%
4 LPM	36%
5 LPM	40%
6 LPM	44%
High Flow Nasal Cannula Flow Rate	FiO ₂
20 LPM to 50LPM	50%
20 LPM to 50LPM	60%
20 LPM to 50LPM	70%
20 LPM to 50LPM	80%
20 LPM to 50LPM	90%
20 LPM to 50LPM	100%
	1

Version: 02-09-2018

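### Daily adverse-event review is required to Day 28 or discharge, but the schedule marks it only to Day 11, and no rule says whether events from the Day-28 call count

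*Combined protocol and SAP*

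**What the plan says.** - **Adverse Event Reporting.** "Investigators will determine daily if any clinical adverse experiences occur", and the period is given as "during the period from enrollment through study day 28 or hospital discharge, whichever occurs first".
- **Appendix 2, Schedule of Events.** The row "Adverse Events Review" has 12 marks, for Days 0 to 11, and its Day-28 cell is blank. A separate row, "Phone Assessment of Disease Outcomes and Adverse Events", is marked at Day 28 only. The table has columns for Days 0 to 14 and Day 28, and none for Days 15 to 27.
- **Premature Withdrawal from Treatment.** "Discharged subjects will receive a 28 day post randomization phone assessment of disease outcomes and adverse events". The section on completion of study drug repeats this for patients discharged from the study hospital.
- **Study Design.** "Patients will be followed to hospital discharge or day 28, whichever comes first". Here the phone contact is described only as confirming that the patient is alive and free of mechanical ventilation.
- **Statistical Considerations, Safety.** AEs are summarized as percentages of patients and numbers of events. No collection window is given, and nothing says whether events first reported in the call are counted.

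**The concern.** The trial describes itself as primarily one of feasibility, safety and proof of concept, so AE data are among its main results. Two things are unsettled.

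First, the text and the schedule disagree about patients still in hospital after Day 11. Site staff usually work from the schedule. The marked days coincide with the dosing days, and the dosing table has patients off drug on Day 12. Under Appendix 2, a patient who completes the full course would have no scheduled inpatient AE review once off drug. The dose rationale gives avoidance of rapid drug withdrawal as the reason for the step-down, so those days are of some safety interest.

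Second, the reporting section places an event after discharge outside the AE period, while the Day-28 call asks about it. Two analysts could fairly include or exclude such an event and report different percentages.

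AE counts also feed a decision. One of the three stopping conditions is an imbalance of more than 4 to 1 in Grade 4 events. If that is read as a ratio of counts, 4 against 1 does not trigger a review and 5 against 1 does, so a single missed or uncounted event can matter.

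**Working it through.** The plan states no figure to reproduce. The check sets the passages side by side and counts days.

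**Is the short AE row real?** In the text read from the PDF, rows in the later part of Appendix 2 come out with 14 cells against 16 day columns in the header. Some columns among Days 12 to 14 were therefore merged or lost in reading. Three observations bear on this:

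1. The AE row has marks in cells 1 to 12 (Days 0 to 11) and none in the last cell.
2. The SpO2/FiO2 row in the same part of the table has the same 12 marks and also keeps a mark in its last cell. The hospital mortality row is marked in that cell too. The last cell is therefore Day 28, and the blank there in the AE row is genuine.
3. The study drug row is marked on the same 12 days, which makes an end at Day 11 look deliberate.

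No mark appears for Days 12 to 14, but those cells should be confirmed on the schedule page itself.

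**Size by day of discharge.** Let *d* be the study day of discharge, with *d* = 28 for a patient in hospital throughout.

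- Last day of daily review under the text: *d*.
- Last day under the schedule: the smaller of *d* and 11.
- Days required by the text but not scheduled: max(0, *d* − 11).
- Days reached only by the Day-28 call: 28 − *d*.

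| Discharge day *d* | Text ends | Schedule ends | Required, not scheduled | Reached only by the call |
|---|---|---|---|---|
| 4 | 4 | 4 | 0 | 28 − 4 = 24 |
| 7 | 7 | 7 | 0 | 28 − 7 = 21 |
| 11 | 11 | 11 | 0 | 28 − 11 = 17 |
| 14 | 14 | 11 | 14 − 11 = 3 | 28 − 14 = 14 |
| 20 | 20 | 11 | 20 − 11 = 9 | 28 − 20 = 8 |
| 28 | 28 | 11 | 28 − 11 = 17 | 0 |

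The 17 days in the last row are Days 12 to 28. Day 28 is included because the withdrawal and completion sections describe the call for discharged patients.

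**What the table shows.** The two problems affect different patients. Long-stay patients lose scheduled review that the text requires. Patients discharged early have most of the 28 days covered by one recall interview, over days that the reporting section leaves outside the AE period.

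**The case against.** The strongest reply is that the explicit rule in Adverse Event Reporting governs, and that it already requires daily review of inpatients to Day 28. On that view Appendix 2 is only incomplete. The reply has force beyond Day 14: with no columns for Days 15 to 27, the schedule could not carry a mark for any procedure on those days, so its silence there is partly a matter of layout. Only the blanks at Days 12 to 14 and at Day 28 can be read directly as conflict. That still leaves an operational table that ends AE review with dosing and has no note carrying it on.

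It can also be said that the Day-28 call follows on from inpatient review and does not compete with it. This largely stands. A reader might count three incompatible AE windows, but daily review in hospital followed by a call after discharge is a sensible sequence, and Appendix 2 lists the call. What remains is that the reporting section ends the period at discharge and the analysis section is silent on call-reported events.

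Finally, intubation and 28-day mortality are outcomes in their own right. Two of the three stopping conditions therefore do not depend on AE review. This is correct and limits the consequence to the Grade 4 count and the AE tables.

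**Conclusion.** The point holds as a mismatch between text and schedule, together with a missing counting rule. The unscheduled days per patient run from 0 (discharge by Day 11) through 3 (Day 14) to 17 (in hospital to Day 28). This assumes that Appendix 2 is followed as marked and that the blanks at Days 12 to 14 are confirmed. It is worth correcting in a trial whose main purpose includes safety, but it does not undermine the design.

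Three stronger readings are tempting, and the documents do not support them:

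- **Most of the follow-up goes unreviewed across the trial.** The long gap applies only to patients with long stays, and no length-of-stay figures are given.
- **Intubated patients are hit hardest.** The withdrawal section follows them to death, Day 28 or discharge, and the schedule gap is the same for anyone still in hospital.
- **AE observation differs between arms.** Nothing in the documents says that length of stay will differ by arm. The risk is conditional: discharge comes after randomization, so if treatment affects it, daily capture in hospital and a single recall afterwards would make crude percentages by arm not fully comparable.

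**What to change.** 1. **Appendix 2:** extend AE review to every inpatient day through Day 28, by added columns or a footnote covering Days 12 to 28, so that it agrees with Adverse Event Reporting.
2. **Adverse Event Reporting:** state that AEs after discharge are captured by the Day-28 call. Align the phone contact described under Study Design.
3. **Statistical Considerations, Safety:** state that AE percentages and counts cover randomization to Day 28 in all randomized patients and include call-reported events. Show inpatient and call-reported events separately, because the intensity of capture differs.

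The cost is a schedule edit, a few sentences of text and modest extra chart review in 30 patients. No dose or clinical rule is touched.

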NOTE: A study day is defined as 24hrs from Randomization, not calendar days. The study calendar window will start with Day 0.

The following dosing schedule will be utilized*:

Dosing Schedule

Version: 02-09-2018

Time following	Number of
Randomization	Breaths
Dose Escalation Phase	
T= 0 Initial Dose	6
T= 4 hours	6
T= 8 hours	9
T= 12 Hours	9
T= 16 hours	12
Maintenance Dose Phase	
T= 20 hours Thru	
Day 7	12
•	
Taper Down Phase	
Day 8 q 6 hours	12
Day 9 q 6 hours	6
Day 10 q 6 hours	4
Day 11 q 6 hours	2
Day 12 Off Drug	

If an increase in dose (during the Dose Escalation Phase) is not tolerated due to worsening hypoxemia, hypotension, or excessive coughing, the subject will be maintained at the previous dose for an additional 4 hours (unless major adverse events leading to premature withdrawal are noted as defined below). If a dose increase (during the Dose Escalation Phase) is again not tolerated the subject will remain on the highest tolerated dose for the remainder of the 7 day treatment period. During the Dose Escalation Phase, a sustained decrease of mean arterial blood pressure (MAP) by 15% or below MAP 65 will result in a decrease of dose to the previous tolerated level. Transient worsening hypoxemia is defined as a decrease in SPO₂ of 7% or more within 15 minutes of treatment for no longer than 15 minutes not associated with coughing or exertion.

If subject develops worsening oxygenation (as defined by need to increase supplemental oxygen to $> 0.50 \; \text{FiO}_2$) at any point in the Taper Down Phase, then dose should be increased to previously tolerated dose that resulted in acceptable oxygenation. Subject should be maintained at that dose for 24 hours and attempt to taper drug downward again should be made. If subject still cannot be tapered downward, then subject will transition out of the trial and consideration given to transition to inhaled lloprost (UNC Hospital formulary inhaled prostacyclin) or epoprostenol.

The Taper Down Phase will begin prior to Day 8 for patients who are able to maintain an arterial oxygen saturation of >90% on room air or for patients for who discharge to home on oxygen is anticipated. If there is a plan to discharge to home, the patient's current dose of inhaled

Version: 02-09-2018

treprostinil or placebo will be reduced by one-half on the day prior to anticipated discharge, and then discontinued on the day of discharge home.

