The following parameters will be measured and recorded using values closest in time to Dose 1 study drug administration on days 0-11 (depending on the specific variable), or until stopping of study drug, whichever comes first. All vascular pressures will be zero-referenced to the mid-axillary line with the patient supine.

- 1) Fluid intake and output (Twenty-four hour net fluid balance)
- 2) Vital signs: Heart rate, systolic and diastolic blood pressure, body temperature, CVP
- 3) Modified Brussels Score data days 0-14:
 - a) Vasopressor use (Y/N), worst systolic BP, creatinine, bilirubin, and platelet count for the day.
- 4) Presence of myopathy
- 5) Frontal Chest Radiograph Lung Injury Score (Days 0, 3, 7 and 28)
- 6) Concomitant medications, including nebulized and inhaled medications.
- 7) Blood banked for future analyses
- 8) Biomarker samples. Plasma obtained from two, 6 ml EDTA anti-coagulated blood samples will be divided immediately after centrifugation into 12 equal 1 ml aliquots in specified tubes and frozen at –80°C. Samples will be temporarily stored in the Pulmonary Division Lab space freezers in Burnett Womack Building or in the Emergency Room freezer. Specimens will be stored in the Koury Oral Health Sciences Building. Reference biomarker list above (Days 0, 3, and 7).

Statistical Considerations/Data Analysis:

Safety

Safety will be assessed via percentage of patients and number of events recorded for the following outcomes:

- Adverse events, serious adverse events, unanticipated problems, study discontinuation overall and due to adverse event, and deaths.
- Cases of dose intolerance, including cases of worsening oxygenation, intractable cough, and systemic hypotension following dosing
- Cases of intubation or noninvasive ventilation for worsening hypoxemia

Percentages of all outcomes above will be provided to the DSMB for regular unblinded review of safety, to be assessed every 6 months or after 15 participants have completed the 28 day trial or been discharged from the hospital (whichever occurs first).

Efficacy

Version: 02-09-2018

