- 2. Any clinically important, untoward medical occurrence that is thought to be associated with the study drug or procedures, regardless of the "expectedness" of the event for the course of a patient with ARDS/ALI.
- 3. The following will be reported as adverse events:
 - Systemic hypotension occurring immediately after and clearly a result of the study drug.
 - Worsening of oxygenation immediately after administration of study drug.
 - Cardiac arrhythmia occurring immediately after administration of study drug.

Expected events for ARDS/ALI are untoward clinical occurrences that are perceived by the investigator to occur with reasonable frequency in the day to day care of patients with ARDS treated in an intensive care unit. Examples of adverse events that are expected in the course of ARDS include transient hypoxemia, agitation, delirium, nosocomial infections, skin breakdown, and gastrointestinal bleeding. Such events, which are often the focus of prevention efforts as part of usual ICU care, will not be considered reportable adverse events unless the event is considered by the investigator to be associated with the study drug or procedures, or unexpectedly severe or frequent for an individual patient with ALI. Examples of unexpectedly

frequent adverse events would be repeated episodes of unexplained hypoxemia. This would be in contrast to an isolated episode of transient hypoxemia (e.g. $SpO_2 \sim 85\%$), related to positioning or movement.

Investigators will report all events to United Therapeutics that are **serious** AND **unexpected** AND **study-related** within 24 hours of becoming aware of the event. The local Institutional Review Board must also be notified in a timely manner. The investigator will then submit a detailed written report to the sponsor, the DSMB, and the Institutional Review Board no later than 5 calendar days after the investigator discovers the event. A written report will be sent to the DSMB within 15 calendar days, and this also passed on to the Institutional Review Board. The DSMB will also review all adverse events during scheduled interim analyses. The written summary of the DSMB's periodic review of adverse events will be submitted to the Institutional Review Board in accordance with standards.

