Patients with ARDS have a high risk of 28-day mortality, which is approximately 45% in general ICU populations. This is because ARDS tends to be part of a syndrome of multi-organ failure that accompanies underlying severe conditions such as septic shock, severe pancreatitis, and multilobar pneumonia in patients with multiple underlying comorbidities. For that reason, 28-day mortality is the most common clinical outcome for large trials of ARDS, and in those large trials, stopping rules for safety or futility are built around 28-day mortality.

This study is a small pilot study of feasibility and safety enrolling patients with early ARDS not yet requiring mechanical ventilation. Due to its small size, a *statistical* stopping rule based on mortality or even Grade IV Adverse events is not possible. This has been confirmed by additional review by the study's statistician. Therefore a *clinical* stopping rule based on Grade 4 events or complete respiratory failure requiring intubation and mechanical ventilation, (an event that is intermediate to possible mortality in ARDS) has served as the stopping rule for this study to date.

The principle conditions for suspension of study enrollment and review of safety by the DSMB will be:

After enrollment of the first 30 patients:

- An imbalance of greater than 4 to 1 (given 2:1 randomization scheme) of any Grade 4 Adverse event from the NIH Common Terminology Criteria for Adverse Events (CTCAE)
- An imbalance of greater than 4 to 1 (given 2:1 randomization scheme) in the number of patients requiring intubation and mechanical ventilation in favor of intervention.
- A 28-day mortality rate of greater than 60% in either study arm, reflecting a rate measurably higher than expected in ARDS.

Of note: To reduce potential bias, the relationship of any Grade 4 or 5 events to study drug will be adjudicated by an expert in pulmonary hypertension and critical care, [name], who is not participating in the study and will be blinded for the assessments.

Version: 02-09-2018

Version: 02-09-2018

References:

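### Only clinically important adverse events have to be recorded, so mild cough, throat irritation, headache, nausea and flushing may be under-counted although tolerability is objective 2

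*Combined protocol and SAP*

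**What the plan says.** Tolerability of inhaled treprostinil is the second objective (Objectives). Adverse Event Reporting has investigators look daily for adverse experiences, then limits what is written down: "If clinically important and unexpected adverse experiences occur, they will be recorded on the adverse event case report form".

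The definition of a reportable event in the same section has three limbs:

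- **Limb 1:** clinically important occurrences that differ from the expected ARDS/ALI course.
- **Limb 2:** "Any clinically important, untoward medical occurrence that is thought to be associated with the study drug or procedures", whether or not the event is expected.
- **Limb 3:** three named post-dose events, namely hypotension, worsening oxygenation and arrhythmia.

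On events expected during ARDS treatment, the section says that they "will not be considered reportable adverse events unless the event is considered by the investigator to be associated with the study drug or procedures"; unusual severity or frequency in a patient also makes them reportable.

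The Safety part of Statistical Considerations summarises recorded adverse events and, separately, "Cases of dose intolerance, including cases of worsening oxygenation, intractable cough, and systemic hypotension following dosing". Risks of Active Study Drug gives the most common effects as cough 54%, headache 41%, throat irritation or pharyngeal pain 25%, nausea 19%, flushing 15% and syncope 6%. On two of these the text following the Dosing Schedule says: "Cough or pharyngitis may occur with the administration of inhaled treprostinil. It is usually mild". It then allows lozenges, throat spray or antitussives so that dosing can continue.

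**The concern.** The effects most likely to decide whether a patient can keep inhaling the drug six times a day are mostly minor ones, and the recording rule is set above them. A patient who coughs after many doses, has a sore throat and a headache, and still completes the course could correctly have nothing on the adverse event form.

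What would be lost is the frequency and grade of the drug's known common effects among patients who stay on treatment. Figures from approved use are a poor substitute. Dose Rationale says that safety in other lung diseases is not established. It also describes going from 6 to 12 breaths within 20 hours, where the recommended regimen starts at 3 breaths and adds 3 breaths at intervals of 1–2 weeks. These symptoms cannot be reliably reconstructed afterwards.

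**Working it through.** **1. Does any route require a mild, tolerated symptom to be recorded?** The plan states no figure on this, so the check is textual.

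- *Limbs 1 and 2:* both require clinical importance. Limb 2 waives expectedness for drug-associated events but keeps importance. The term is not defined.
- *Limb 3:* none of the five symptoms is named.
- *Exception for attributed or unusual events:* this restores events that would otherwise be set aside as expected in ARDS. It does not remove the importance test in limb 2.
- *Dose intolerance (Safety; Data Safety Monitoring Board):* the list is illustrative, so a dose-limiting headache or nausea could count. A symptom that does not limit dosing is not dose intolerance.
- *Hold rule:* "If an increase in dose (during the Dose Escalation Phase) is not tolerated due to worsening hypoxemia, hypotension, or excessive coughing" triggers a hold at the previous dose. It does not concern tolerated symptoms.
- *Withdrawal rule:* "Severe, intractable cough resulting in worsening hypoxemia and prolonged increase in" oxygen requirement sets a high bar.
- *Unanticipated Problems:* reported regardless of severity, but they must be unexpected and suggest greater risk than was known. Listed effects would normally fail both tests.
- *Adverse Events Review (Appendix 2, Days 0–11) and the Day 28 phone assessment:* neither names symptoms or sets its own recording threshold.
- *Concomitant medications:* these may reveal a treated symptom, but not an untreated one and not its grade.

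No route requires it. Recording is permitted, not demanded.

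**2. Scale.** Inputs: 30 patients at 2:1 (Study Design), so about 20 active and 10 placebo; rates from Risks of Active Study Drug, assumed to transfer. Expected active patients = 20 × rate; chance of at least one = 1 − (1 − rate)^20.

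| Symptom | Rate | Expected of 20 | P(at least one) |
|---|---|---|---|
| Cough | 54% | 10.8 | >0.999 |
| Headache | 41% | 8.2 | >0.999 |
| Throat irritation | 25% | 5.0 | 0.997 |
| Nausea | 19% | 3.8 | 0.985 |
| Flushing | 15% | 3.0 | 0.961 |

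The documents do not give the share that would be mild. The unrecorded number therefore runs from zero up to these counts and cannot be narrowed.

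**3. What solicited recording would deliver.** Exact (Clopper-Pearson) 95% intervals with n = 20:

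- 3/20 (15%): 3.2–37.9%
- 5/20 (25%): 8.7–49.1%
- 8/20 (40%): 19.1–63.9%
- 11/20 (55%): 31.5–76.9%

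The documents give no placebo rates, so 0% to 40% is assumed. Newcombe 95% intervals for active minus placebo, 20 against 10:

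- 3/20 v 0/10: 15 points (−14 to 36), half-width 25
- 8/20 v 2/10: 20 points (−16 to 46), half-width 31
- 11/20 v 4/10: 15 points (−20 to 45), half-width 33

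Rates within an arm would be rough but usable. Between-arm differences would be descriptive only.

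**The case against.** The best defence is that this is a deliberate reporting standard for acutely ill patients. Tolerability is also read from dose intolerance, discontinuation overall and due to adverse events, and intubation or noninvasive ventilation, all tabulated in Safety. Investigators look daily for any adverse experience, a respiratory therapist oversees dosing, and concomitant medications are logged. A cough treated so that dosing can continue might well be judged clinically important. The adverse event form and the DSMB charter are not among the documents, and the form may already list these symptoms. Intervals from 20 patients are wide, and cough or headache in acute respiratory illness is not all drug effect.

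Most of this stands as a limit on the point. It shows that the more consequential events are captured and that some mild ones will be. It does not show that mild, tolerated symptoms must be recorded.

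Three stronger readings are tempting and are not supported:

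- *Cough goes unnoted once escalation ends.* A reader might infer this because the hold for excessive coughing applies only in the Dose Escalation Phase. That rule governs dosing, not recording, and the dose-intolerance outcome is not limited to that phase.
- *Events below Grade 4 are not graded.* Study Stopping Rules refers to "any Grade 4 Adverse event from the NIH Common Terminology Criteria for Adverse Events (CTCAE"), but identifying a Grade 4 event presupposes grading. Silence elsewhere does not show that lower grades are omitted.
- *The treatment comparison is biased.* The same threshold applies to both arms under blinding, so gross bias is unlikely.

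**Conclusion.** The point holds in a limited form. As written, the plan does not require mild, non-dose-limiting cough, throat irritation, headache, nausea or flushing to be recorded, so the adverse event percentages may understate the drug's commonest effects in a trial with tolerability as an objective. Serious events, Grade 4–5 events, dose-limiting events and post-dose hypotension, desaturation and arrhythmia are covered. No stopping rule or efficacy analysis depends on the gap.

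The size is unknown: from none to about 3 (flushing) or 11 (cough) active patients per symptom, if approved-use rates transfer. The conclusion assumes that the unseen form does not already solicit these symptoms and that investigators apply the importance test as written. It is a cheap improvement worth making, not a threat to the trial's validity.

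**What to change.** In Adverse Event Reporting, add a CTCAE-graded checklist of five items (cough, throat irritation or pain, headache, nausea, flushing) to the existing daily review. Complete it in both arms, once before the first dose and then daily while on study drug, regardless of clinical importance or presumed cause, with a not-assessable option.

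In the Safety analysis, report by arm the percentage of assessable patients with each symptom new or worse than the pre-dose baseline, by grade, with exact confidence intervals. Label between-arm differences as descriptive. Leave the threshold for other events and the expedited reporting rules unchanged.

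Study Stopping Rules describes its rule as already in use, so enrolment may have begun. If so, apply the checklist prospectively and report solicited and unsolicited patients separately; the solicited group would then be smaller than 20 and 10. If the form already carries such a list, one sentence in Adverse Event Reporting saying so is enough.

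Cost: 5 items × 13 checks (one pre-dose plus Days 0–11) = 65 entries per patient at most, or 65 × 30 = 1,950 in all; fewer where drug stops early. Some patients will not be able to self-report, since Justification of Including Vulnerable Subjects expects impaired capacity to be common, although exclusion 19 (unable to complete the breathing maneuver) limits this. Absolute rates will still partly reflect the underlying illness, which the baseline comparison reduces but does not remove.
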